Parkinson's disease (PD) affects 1-2% of people over age 65, representing over 1 million Americans.¹ Although traditionally characterized by its motor symptoms, over the course of PD cognitive symptoms have a greater impact on patient suffering and caregiver burden.² Three-fourths of patients surviving 20 years or longer develop dementia making it the leading cause of nursing home placement.³ Despite the high prevalence of cognitive dysfunction in PD, its pathophysiology is poorly understood and current treatments have minimal effects on symptoms or progression.⁴ Moreover, standard medical and surgical PD treatments have no effect on cognition and may in fact worsen cognition.⁵ *Better treatment strategies for PD-related cognitive dysfunction based on an improved knowledge of neurobiological mechanisms are clearly needed.*

Functional connections between cortical regions are important for normal cognition and memory^{6, 7} and that alterations in functional cortical connectivity may contribute to cognitive dysfunction in PD.⁸ In the past decade, modern network theory has emerged as a powerful tool to describe the organization of functional brain networks using the mathematics of graph theory.⁹ Two fundamental measures are path length, defined as the average distance between any two nodes in a network and a measure of global efficiency and integration; and the clustering coefficient defined as the average number of mutually connected nodes surrounding each node and a measure of local efficiency and modularity. Figure 1 shows an optimal balance between global and local efficiency can be achieved through clustered modules connected through integrating links, a design termed small-world architecture.¹⁰ It is well-established that healthy brain networks demonstrate small-world architecture.¹¹ Importantly, loss of small world features are associated with cognitive dysfunction in multiple sclerosis and Alzheimer's disease (AD).¹²⁻¹⁴ Known features of PD neurophysiology relevant to network connectivity include reduced cortical inhibition¹⁵, which may lead to disrupted modularity, and pathological subcortical oscillations¹⁶, which may drive increased randomness. *Our pilot data and other studies¹⁷ suggest that network architecture is abnormal in PD but its relationship to cognitive dysfunction has not been examined.*

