MEG Data Processing: Following data acquisition, there are 4 major steps for graph theory analysis.⁶³ First, data will be transformed into the frequency domain using Morlet wavelets and parceled into six standard frequency bands: delta (1-4 Hz), theta (4-8 Hz), alpha (8-12 Hz), low beta (12-20 Hz), high beta (20-30 Hz) and gamma (30-60 Hz).¹¹⁰ Further analyses will be performed separately for each band. Second, the strength of functional connectivity must be calculated between all sensors. Granger causality will be used for this step, providing a directional weighted measure of connectivity suitable for graph theory.^{111, 112} Third, functional connections between nodes will be used to create a network graph. This is matrix representing the directed weighted connection strengths between all sensors for each frequency band. Advantages of creating a weighted network graph include ensuring full connectedness and avoiding potentially arbitrary thresholds required for binary networks.⁶¹ Finally, graph analyses can be performed on the network graph using the Matlab-based Brain Connectivity Toolbox⁶¹ and custom Matlab code. Our *primary MEG outcome measure* will be network small-worldness, calculated as the ratio of the mean clustering coefficient to the mean path length normalized to a randomly connected network.¹¹³ *Planned secondary MEG outcome measures* will include global efficiency (a measure of global integration related to path length), nodal efficiency (a measure of modularity)⁶⁰, and degree distribution (a measure of network resilience)¹¹⁴.

B. Description of Population to be Enrolled:

We will enroll 25 PD subjects over the age of 40 without cognitive impairment diagnosed with probable PD using UK Brain Bank Criteria³⁸ and 55 PD subjects over the age of 40 with MCI or mild dementia using the Movement Disorder Task Force 2012 criteria and a Clinical Dementia Rating scale score (CDR) less than 2.^{39, 40} All study visits will be performed in subjects' best dopaminergic On state. PD MCI and mild dementia subjects will be tested on anticholinesterase therapy if already taking these medications given the potential difficulty of finding drug naïve subjects; long half-life of these medications; and desire to find measures robust to medication effects as seen in prior MEG studies.⁴¹

Exclusion criteria:

- 1) features suggestive of other neurological disorders
- 2) DBS
- 3) evidence for active depression or Hospital Anxiety Depression Scale⁴² score \geq 11

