- 4) motor symptoms expected to interfere with scanning
- 5) contraindications to TMS:
 - history of seizures or status epilepticus,
 - unstable coronary artery disease
 - hydrocephalus
 - implantable electrodes, cerebral spinal fluid shunts, skull plates or other intracranial metal
 - medical devices including pacemakers or other implantable stimulators or pumps
 - subjects taking medications known to lower seizure threshold
 - pregnancy

In order to complete recruitment including consent screen failures, drop-outs and unusable datasets we request the capacity to recruit up to 150 participants.

C. Study Design and Research Methods

Aim 1 Rationale and Design: Even while not engaged in a task the brain exhibits spatially and temporally organized patterns of activity.⁸⁴ The past 15 years has seen remarkable progress in understanding these intrinsic functional networks (also termed resting-state networks) in both health and disease.⁸⁵ Intrinsic networks are consistent within and across individuals, correlate with behavioral and clinical outcomes, and can be analyzed with graph theory measures to define global and local aspects of network organization.⁵⁹ MEG can be used to identify multiple intrinsic networks similar to fMRI but with additional information regarding the power spectra of connections.^{86, 87} Importantly, MEG measures of intrinsic activity can sensitively discriminate AD from other neurological disorders and correlate with cognitive function in both AD and multiple sclerosis.^{40, 47, 64} Prior studies of PD suggest changes in cortical connectivity may be associated with dementia but did not define network organization using graph theory.⁸⁸ Our *objective* for this experiment is to determine whether graph theory measures of intrinsic MEG activity correlate with cognitive dysfunction in PD. We *hypothesize* that loss of small-world architecture contributes to cognitive dysfunction in PD through loss of local efficiency and increased randomness. To test this hypothesis, 25 PD subjects with MCI and 25 with normal cognition will undergo neuropsychological testing and a resting MEG scan for analysis for this aim. MEG and neuropsychological testing may be done on the same day or separate days, not to exceed 1 week in between. We will use graph theory measures to model the

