relationship between network connectivity and cognitive function. The data generated by this Aim will fundamentally advance our understanding of the role of cortical physiology in PD cognitive dysfunction, will provide a modern network framework for future studies in this field and may provide insights leading to future therapeutic targets.

Aim 2 Rationale and Design: While finding group differences or clinical associations in brain connectivity using MEG will improve our understanding of the pathophysiology of PD cognitive dysfunction it is unlikely to provide sufficient discriminant ability to serve as a useful diagnostic or predictive biomarker. Machine learning algorithms offer several advantages in terms of biomarker development including: 1) Characterization of data at the level of the individual; 2) Ability to simultaneously optimize multiple features from complex datasets; and 3) Allows data to drive feature selection rather than theoretical assumptions.⁷² Support Vector Machine (SVM) is a machine learning method that works by determining the maximum separation between classes in a high dimensional space composed of the features of interest.¹¹⁹ Our *objective* for this Aim is to develop a novel state-defining biomarker for PD-MCI based on MEG measures of regional activity and network connectivity using SVM. We *hypothesize* that cognitive dysfunction in PD can be characterized through a unique combination of MEG regional and network features and optimized through SVM. To test this hypothesis, we will reanalyze the MEG data collected in Aim 1 using SVM to classify PD patients with and without MCI.

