AIM 1 Statistical Analysis and Sample Size: To address our primary research question, Spearman correlations will be used to identify frequency spectra small-worldness measures associated with the MDRS in eyes-closed data with a false detection rate set at 0.05 to handle the issue of multiple comparisons. We will then use linear regression to determine whether small-worldness in these specified frequency bands remain associated with the MDRS when controlling for each other as well as other important covariates, namely age and motor severity. A *sample size* of 45 (allowing for 5 drop-outs and/or unusable data-sets from the original 50) will allow us to detect correlations of 0.18 or higher between our MEG features and MDRS with 80% power 0.05 significance. This is comparable to correlations of 0.19 and higher seen in other resting state MEG studies of cognition.¹¹⁵ Planned secondary analyses will parallel our primary analysis to determine whether global efficiency, nodal efficiency or degree distribution are significantly associated with MDRS in linear regression models. Exploratory analyses will assess reactivity of these measures between eyes open and closed conditions and assess whether domain specific neuropsychological test scores are associated with connectivity within networks defined by domain related nodes (e.g. occipital nodes and visuospatial tests).

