AIM 2 Statistical Analysis and Sample Size: We will use SVM to determine what combination of MEG features yields the most robust classifier for discriminating PD with and without MCI. The principle behind SVM learning is that features of interest can be modeled in a high-dimensional feature space (see Figure 2 for a visualization of a very simple 2 feature space). SVM then uses a recursive algorithm to define a hyper-plane of select features creating the greatest distance between groups of interest.¹¹⁹ Given the large potential combination of MEG features and sensors this will be a computationally intensive but tractable SVM application. As the optimal number of features to build an SVM classifier is not known a priori, we will use a procedure called bagging-cross-validation to determine the optimal number of features and maximize the information gained from SVM in this relatively small sample size.¹²¹ This approach uses a boot-strap leave one out procedure to create $n - 1$ training sets and n test subjects, where n is the total sample size, to optimize feature number and maximize the final receiver operating curve. Given the large effect sizes seen in our pilot data and other MEG studies of PDD⁵⁸, we anticipate that our *sample size* of 45 (allowing for 5 unusable data-sets from the original 50) will allow us to create a classifier with an area under the ROC curve (AUC) of 0.95 or higher comparable to AUCs seen in other SVM applications in dementia and MCI populations with as few as 15 subjects per group.⁶⁸

AIM 3 Statistical Analysis and Sample Size: We will address our primary clinical research question by determining whether there is a significant group difference between the real and sham treated PD-MCI patients on the MDRS change following rTMS using repeated measures ANOVA. We will address our primary physiologic research question by determining whether there is a significant difference between the real and sham treated PD-MCI patients on change in MEG measures of small-worldness using a repeated measures ANOVA. Planned secondary analyses will include determining group differences in change on measures of quality of life, domain specific neuropsychological results and durability at the 28-day post-TMS time point. If cognition is improved we will use regression modeling to determine if these improvements were associated in changes

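### Aim 2 has no age-and-motor-score reference for its MEG classifier, so part of its AUC could reflect those differences rather than cognitive state

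*Combined protocol and SAP*

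**What the plan says.** **Aim 2.** Section IV.C (Aim 2 Rationale and Design) gives the objective as to "develop a novel state-defining biomarker for PD-MCI based on MEG measures of regional activity and network connectivity using SVM", and the method as "we will reanalyze the MEG data collected in Aim 1 using SVM to classify PD patients with and without MCI". Section IV.F (Aim 2 Statistical Analysis) describes the inputs: "We will use SVM to determine what combination of MEG features yields the most robust classifier for discriminating PD with and without MCI". It specifies bootstrap leave-one-out resampling, 45 usable data sets out of 50, and an anticipated AUC of at least 0.95. It mentions neither age nor motor severity.

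**Groups.** Section IV.C (Aim 1) states that "25 PD subjects with MCI and 25 with normal cognition will undergo neuropsychological testing and a resting MEG scan". Section IV.B sets the same lower age bound for both groups, beginning "We will enroll 25 PD subjects over the age of 40 without cognitive impairment diagnosed with probable PD". The exclusions that bear on disease stage are DBS and motor symptoms likely to disturb scanning. No matching or stratification on age or motor severity is described.

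**Aim 1.** On the same recordings, Section IV.F tests whether small-worldness stays associated with the MDRS when "controlling for each other as well as other important covariates, namely age and motor severity".

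**Motor score.** Section IV.A says in general terms that the UPDRS motor section is collected as a covariate for disease severity. The Aim 2 text does not take this up, and the sentence does not cover age.

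**The concern.** A data-driven classifier uses whatever separates the two groups. If the impaired patients are older or have worse motor disease, MEG features that track age or motor severity will help to classify them even if they carry nothing about cognition. The protocol gives some reason to expect this. Section II presents cognitive decline as something that accrues over the disease ("Three-fourths of patients surviving 20 years or longer develop dementia") and suggests that PD pathophysiology such as subcortical oscillations may itself disturb network organisation.

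Leave-one-out resampling does not help. It guards against overfitting, but each held-out subject comes from the same two groups, so any imbalance passes through to the test predictions.

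What is at stake is the meaning of the result. The aim is a biomarker of cognitive state. Without knowing how well age and a motor score separate the same patients, a reader cannot tell how much of the AUC needed MEG.

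**Working it through.** **Inputs from the protocol.** 45 analysed subjects (taken as 22 and 23) and an anticipated AUC of 0.95 (Section IV.F, Aim 2).

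**Assumed inputs.** The protocol gives no age or motor score by group. I assume normal distributions with equal variance and gaps of 0.5 to 1.0 SD.

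**1. The plan's own figure.** The 0.95 is an expectation drawn from pilot data and cited work. No null value, effect size or power accompanies it, so there is nothing to reproduce. It can be converted. With AUC = Φ(D/√2), where D is the standardised separation, 0.95 needs D = √2 × 1.645 = 2.33.

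**2. AUC from the covariates alone.** For one covariate, D = d. For two covariates with equal gaps d and within-group correlation r, D = d√(2/(1 + r)). At r = 0 the AUC is then Φ(d).

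| Gap d (SD) | One covariate, Φ(d/√2) | Two, independent, Φ(d) |
|---|---|---|
| 0.5 | 0.64 | 0.69 |
| 0.8 | 0.71 | 0.79 |
| 1.0 | 0.76 | 0.84 |

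At d = 1.0 and r = 0.5, D = √(2/1.5) = 1.155 and the AUC is Φ(1.155/√2) = Φ(0.816) = 0.79.

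**3. How much could reach the MEG classifier.** The table shows what a covariate-only classifier would score. MEG tracks these variables imperfectly. If MEG features carry each of two independent covariates with correlation 0.5, each gap halves and the AUC is Φ(0.5d), which is 0.60, 0.66 and 0.69 for d = 0.5, 0.8 and 1.0.

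**4. Comparison with 0.95.** Even two independent 1.5-SD gaps give D = 1.5 × √2 = 2.12 and AUC = Φ(1.5) = 0.933, short of 0.95.

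**5. Would a baseline comparison settle it?** At about 22.5 per group, a two-sided 5% test has 39% power for a 0.5-SD imbalance and 77% for 0.8 SD. A non-significant result would not rule out an imbalance that matters.

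**6. Precision of the proposed comparison.** Take a MEG AUC of 0.85 against a reference of 0.76 as an example. The Hanley-McNeil standard errors are about 0.06 and 0.07. With an assumed correlation of 0.3 between the two estimates, the SE of the difference is √(0.06² + 0.07² − 2 × 0.3 × 0.06 × 0.07) = 0.077. The 95% half-width is 1.96 × 0.077 = 0.15, around a difference of 0.09.

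**The case against.** The strongest reply is that the imbalance is hypothetical. The protocol does not say that the groups are unmatched; it is silent. The 20-year figure concerns dementia in long survivors, whereas Aim 2 separates patients with and without MCI, and the two exclusions noted above may narrow the range of disease stage in both groups. This stands. A reader might infer that the groups are known to differ, but the documents support only that no matching is described.

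A reader might also infer that the whole of a high AUC could be an age or stage effect. Step 4 shows otherwise for the anticipated 0.95 under moderate gaps. The concern bites mainly if the achieved AUC is lower, for example 0.75 to 0.85, where a covariate-only classifier could plausibly score about the same.

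Nor is it right that nothing in the plan bears on the question. Aim 1's adjusted regression for small-worldness, with parallel secondary analyses for the other network measures, is partial evidence on whether the network signal survives adjustment. It does not show what a multi-feature SVM, which also uses regional activity, has learned.

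Finally, Aim 2 is small-sample biomarker development and does not touch the randomised comparison in Aim 3. That limits the weight of the point but does not remove it.

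**Conclusion.** The concern holds as a missing comparator. Aim 2 uses MEG features alone, describes no matching on age or motor severity, and neither adjusts for nor compares against two variables that Aim 1 controls for in the same recordings. The general UPDRS statement in Section IV.A does not close the gap.

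The size is conditional. For gaps of 0.5 to 1.0 SD, age or motor score alone would give an AUC of 0.64 to 0.76. Two 1-SD gaps together would give 0.84 if independent and about 0.79 if correlated at 0.5. The share reaching a MEG classifier would be smaller. These figures rest on assumed gaps and normal distributions, not on trial data. They support saying that part of the AUC could reflect age or motor severity. They do not support saying that it does, or that moderate gaps could account for 0.95.

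**What to change.** In Section IV.F (Aim 2 Statistical Analysis):

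- Add a reference classifier using only age and UPDRS motor score, run within the same cross-validation and on the same subjects.
- Report the MEG AUC, the reference AUC and their difference with a confidence interval, and interpret the biomarker claim in light of that difference. A pass/fail rule is not advisable: with a half-width near 0.15 in the example above, a real increment could fail it.
- Optionally, rerun the SVM with age and UPDRS motor score regressed out of each MEG feature within each training set. Label this a sensitivity analysis only. Motor and cognitive severity may share a cause, so the step can remove real signal.
- If matching is intended, state it in Section IV.B. The comparator remains useful either way.

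Years since diagnosis would be a natural third reference variable, but the documents do not list it as collected, so the fix does not depend on it.

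The cost is modest extra analysis with no added subjects, visits or scans. The interval will be wide at n = 45, and the headline AUC may look less favourable beside its reference.

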AIM 3 Rationale and Design: rTMS can improve cognition in PD without dementia⁵², PD with depression⁸⁰, older adults¹²² and in AD¹²³ but has not been tested in PD-MCI. Given the need for improved cognitive treatments and possible differences in rTMS effects on PD-MCI pathophysiology it is important to specifically test rTMS in this population. Prior studies as well as our own pilot data suggest that rTMS modulates cortical connectivity,^{16,17} thus rTMS provides not only a potentially effective intervention but an important causal test of our associative data and theoretical link between cortical connectivity and cognitive dysfunction in PD. Our *clinical objective* for this experiment is to determine whether rTMS improves cognitive outcomes in PD-MCI. Our *mechanistic objective* is to determine whether rTMS normalizes patterns of cortical connectivity. We *hypothesize* that high-frequency bifrontal rTMS will partially normalize patterns of cortical connectivity linked to frontal nodes and will improve cognitive measures. To test this hypothesis 55 PD-MCI subjects will be randomized to a 10-day course of real or sham bifrontal high frequency rTMS. We will measure cognitive and MEG outcomes pre-treatment and on the day of the last treatment (neuropsych testing and MEG procedures may be separated by 1 day if patient is fatigued) and repeat cognitive measures 28 days post rTMS to assess the durability of cognitive changes.

TMS: TMS will be administered using a 70-mm diameter air-cooled figure-of-8 coil and SuperRapid² Magstim Stimulator. We will first define the subject's resting motor threshold (MT) by localizing the hand area of motor cortex and determining the minimal TMS amplitude needed to produce a motor-evoked potential of 50 microV on 4 of 8 trials measured by EMG over the first dorsal interosseous muscle (Biopac, Goleta, CA). Once the MT is determined, repetitive pulses will be delivered to the right and left pre-frontal cortex (Brodmann area 46) using a frameless stereotactic navigation system and the subject's MRI in Brainsight software. Depending on our preliminary results from Aim 1, we may change our target if it is evident that a particular frontal node shows high clustering within beta or theta frequency bands. This type of targeting based on functional data has been previously performed and may enhance TMS effects on intrinsic connectivity.¹⁶ Stimuli will be delivered at 20 Hz at 90% rMT for 25 trains of 30 pulses per train, inter-train

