interval of 30 seconds for a total of 750 pulses per hemisphere, which is well within the most recent international TMS safety guidelines.¹²⁹ This dose and duration of rTMS is based on physiological studies of healthy adults and treatment studies of cognition in PD and Alzheimer’s disease.^{52, 123} Side of first stimulation (left vs right hemisphere) will be counterbalanced across subjects. Sham stimulation will be delivered using a sham coil fitted with electrodes to mimic both the auditory and somatic sensation of real TMS as I have performed in prior TMS trials.¹⁹

Schedule of Procedures

	Baseline Procedures ²	← 2 weeks →			28 days post-rTMS Session 10 ¹
		rTMS Session 1 ¹	rTMS Sessions 2-9 ¹	rTMS Session 10 ¹	
Informed consent	X				
MRI (anatomical and optional functional scans)	X				
MEG	X			X ¹	
Neuropsych tests	X			X ¹	X ¹
rTMS (real or sham) ¹		X ¹	X ¹	X ¹	
Randomization to real or sham TMS ¹	X				

¹PD-MCI subjects only

²Baseline procedures to be completed within 1 week of rTMS Session 1

D. Description, Risks and Justification of Procedures and Data Collection Tools:

PD-MCI and mild dementia patients may be considered a vulnerable population due to cognitive dysfunction but are necessary to answering our research questions. We are cognizant of this issue and will carefully assess potential participant’s understanding of the study, particularly of study activities and risks. If there are any concerns on the part of the investigator or potential participant, we will require that their guardian participate in the consenting process and sign an informed consent. We will also require that PD-MCI subjects give consent, or at minimum assent if fully informed consent is not possible. Our protocol and consent forms will be approved by our local IRB before approaching any potential subjects.

After enrollment and screening assessment, PD and PD-MCI subjects will undergo neuropsychological testing, magnetoencephalography (MEG) recordings, and MRI. PD-MCI subjects will then be randomized in a 1:1 ratio to real or sham TMS groups using MAPLE 9.0 software (Waterloo, Canada). Baseline neuropsychological testing, MEG, and MRI may be performed over multiple days, but all will be completed within 1 week and within 1 week of first TMS session for PD-MCI subjects.

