TMS will consist of 10 sessions (over two weeks) of 20 Hz repetitive TMS given at 90% of motor threshold in 25 trains of 30 pulses per train with a 28.5 second inter-train interval to each prefrontal cortex (Brodmann area 46) localized using MRI andBrainsight software. There will be a total of 750 pulses per hemisphere per session. These TMS parameters are well within the most recent published safety guidelines.¹²⁹ This dose and duration was chosen on the basis of prior physiological studies in healthy adults⁷⁸ and in treatment studies of cognition in PD⁵² and Alzheimer's Disease.¹²³

There are minimal risks involved in the proposed research. There are no known risks from MEG recordings. In appropriately screened subjects, the primary risk of MRI is claustrophobia and anxiety which is remediable by removal from the scanner. Cognitive testing as proposed in this study may induce boredom or restlessness. Any new neuropsychiatric diagnoses detected during screening (e.g. depression) will be referred for appropriate treatment, including emergent treatment if indicated. TMS as proposed in this study has a minimal risk (less than 1 in 1000) of inducing seizures in appropriately screened subjects or other adverse events.¹²⁹ Notably, there have been no cases of epilepsy (recurrent seizures) or status epilepticus (prolonged seizure considered a medical emergency) with TMS. The risks of TMS in PD are similar to that of the general population.³ Transient motor worsening has been reported with supplementary motor area TMS in PD, but not with the frontal targets we have proposed. There have been reports of hearing loss with repeated TMS pulses and thus all subjects will be required to wear ear plugs, similar to MRI. There is a slight risk of headache and neck pain which is typically self-resolving and/or treatable with over the counter analgesics.

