All subjects will be required to wear hearing protection and will be supervised by study personnel during all aspects of this study. A neurologist will be available either in person or on-call within the building in the event of a seizure or other adverse study event. Study personnel involved in human subject interactions will be trained not only in human subjects protection but will be also BLS or ACLS certified and specifically trained in seizure safety and what to do in the event of other medical emergencies. There is a COR cart available outside of the TMS and MEG laboratories. All adverse events will be reported to the IRB within 5 days and seizures or other significant adverse events associated with TMS will additionally be reported to the FDA.

E. Potential Scientific Problems:

Prior TMS trials are often questioned regarding the adequacy of patient blinding with certain sham procedures. Our sham involves both auditory and tactile stimulation, and in fact resulted in a similar improvement in depression as real TMS in our recent trial.¹⁹ Subject retention, particularly with PD-MCI, may be difficult with 2 weeks of daily treatment. We will use similar procedures to our PD apathy rTMS trial where we maintained 100% retention. Finally, our sample size is relatively small to detect clinically significant changes. This is in part due to budgetary limitations and one goal of this trial is to serve to develop a more definitive, larger trial with longer-term follow-up. Changes in sensor location over repeated recordings may result in false attribution of brain activity

changes. To address this issue, sensors will be realigned to a common sensor array to allow repeated group level analysis in a shared brain space.¹⁰⁹

F. Data Analysis Plan:

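### Aim 3 has no outcome-collection rule for randomised patients who stop rTMS early, so both primary comparisons tend towards treatment completers

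*Combined protocol and SAP*

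**What the plan says.** Section IV.C, Aim 3 Rationale and Design, sets the post-treatment assessment: "We will measure cognitive and MEG outcomes pre-treatment and on the day of the last treatment". The only flexibility is that "neuropsych testing and MEG procedures may be separated by 1 day if patient is fatigued". The same sentence then plans to "repeat cognitive measures 28 days post rTMS to assess the durability of cognitive changes".

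The Schedule of Procedures in the same section marks the post-treatment MEG and neuropsychological tests in the column for Session 10. It labels the follow-up column "28 days post-rTMS Session 10".

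Section IV.E raises the risk of loss: "Subject retention, particularly with PD-MCI, may be difficult with 2 weeks of daily treatment". Its answer is prevention: "We will use similar procedures to our PD apathy rTMS trial where we maintained 100% retention".

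In section IV.F, Aim 3, the primary clinical question is the group difference "on the MDRS change following rTMS using repeated measures ANOVA". The primary physiologic question is the same comparison for MEG small-worldness. The sample size starts from 55 patients, removes 5 as drop-outs, and plans on 25 per group.

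**The concern.** Both post-treatment time points depend on how much stimulation the patient receives, which is determined after randomisation. The protocol does not say whether or when a patient who stops early is assessed. It has no early-termination visit, no assessment day fixed by the calendar, no definition of the analysis population and no missing-data method.

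The visit at risk carries both primary endpoints, and it is the only post-treatment MEG. A repeated measures ANOVA in its usual form uses only patients with both a baseline and a post-treatment value, so a stopper with no later value drops out of the comparison. If stopping is related to both arm and outcome, the real-minus-sham difference no longer rests on randomisation. Analysis cannot recover an assessment that was never made. A stopper who is assessed on the last day of stimulation has a shorter interval since baseline than everyone else, and the 28-day visit also moves earlier.

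**Working it through.** **Where the two anchors agree and where they part**

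| Patient | Aim 3 text | Schedule of Procedures |
|---|---|---|
| All 10 sessions, on time | Day of Session 10; follow-up 28 days later | Same |
| All 10 sessions, finishing late | Day of the late Session 10; follow-up 28 days later | Same |
| Stops after, say, Session 4 | Day of Session 4, which is 10 − 4 = 6 sessions early and usually past once stopping is known; follow-up counted from then | Session 10, which does not occur; follow-up counted from an event that does not occur |

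Only the third row is a problem.

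**The plan's own figures (section IV.F, Aim 3)**

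- Standardised effect: 10/13 = 0.77, as stated.
- Allowed loss: 5/55 = 9.1%.
- Power at 25 per group, two-sided 0.05: 77.6% (normal approximation) or 76.0% (t-test), against the stated 80%. Sidedness is not stated; one-sided, the figures are 85.9% and 85.0%. The two-sided t-test gives 80.0% at 27.5 per group, that is, with all 55 measured. The shortfall is a separate matter and the present point does not depend on it.
- Standard error of the difference: 13 × √(2/25) = 3.7 points.

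**Possible bias from analysing completers only**

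Let n be the number randomised per arm (55/2 = 27.5 under 1:1 allocation). Let k be the number of unmeasured stoppers in an arm, and D the amount by which their MDRS change would have been worse than that of the arm's completers. Leaving them out raises that arm's mean by (k/n) × D. The bias in the difference is the real-arm shift minus the sham-arm shift. The documents do not give D or the split of losses; both are assumed.

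- All 5 in one arm, D = 5: (5/27.5) × 5 = 0.9 points.
- All 5 in one arm, D = 10: (5/27.5) × 10 = 1.8 points, 18% of the 10-point target.
- All 5 in one arm, D = 13: (5/27.5) × 13 = 2.4 points, 24% of the target.
- Split 3:2, same D in both arms: (1/27.5) × 10 = 0.4 points to (1/27.5) × 13 = 0.5 points.
- Losses balanced and unrelated to outcome: no bias, only lost information.

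With stoppers worse than completers, losses mainly in the real arm inflate the difference and losses mainly in the sham arm shrink it. The documents give no SD for small-worldness, so the same calculation cannot be made for the MEG endpoint.

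**What measuring stoppers would do to power**

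Assume all 55 are measured, the SD is 13, 5/55 of the real arm stop early, and these stoppers keep a fraction f of the 10-point effect. The expected difference is 10 × (50 + 5f)/55, which is 9.1 at f = 0 and 10.0 at f = 1. Two-sided t-test power runs from 72% to 80%, and is 76% at f = 0.5. The 50 completers alone also give 76.0%.

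**The case against.** The best defence is that text and table do not conflict. The Aim 3 text has just described a ten-day course, and section IV.D gives ten sessions over two weeks, so the last treatment naturally means Session 10. This stands. A reader might infer a contradiction between the two, but they name the same day for every completer, including one who finishes late after missed sessions. The gap is one missing rule for a patient whom neither place addresses.

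A reader might also infer that early stoppers provide no data, or that the plan restricts the analysis to completers. The documents state neither. That nothing is collected follows only from a literal reading of the table. A site could take the Session 10 column, which sits under a two-week span, as the planned end of week two, and the Aim 3 wording could support an assessment on the last day actually treated. Section IV.F compares real-treated with sham-treated patients and names no completers-only population. What remains is that no rule settles which of these a site should do.

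On frequency, section IV.E says only that retention may be difficult, and it cites full retention in an earlier rTMS trial. That lowers the likely number of stoppers but gives no rule for those who occur. The 5 allowed drop-outs may also be study withdrawals, whom no assessment rule would recover.

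On size, the upper figures need every loss in one arm and a gap as large as the whole target effect or one full SD. Even then the shift is 1.8/3.7 to 2.4/3.7, about 0.5 to 0.6 of a standard error. It is systematic, however, and a larger sample would not remove it.

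Measuring on the last day of stimulation is a defensible choice for a mechanistic MEG endpoint, and the fix should leave it in place for completers.

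**Conclusion.** The point holds as a missing outcome-collection rule after early discontinuation. Followed as written, the plan leaves a stopper's primary MDRS and MEG either mistimed or without a scheduled day, and the 28-day visit with them.

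The possible bias in the MDRS difference is about 1.8 to 2.4 points in the worst case, about 0.4 to 0.5 with a 3:2 split, and zero if losses are balanced and unrelated to outcome. These figures rest on the plan's 5 losses in 55, on those losses being early stoppers who are never measured, and on an assumed gap of 10 to 13 points. The documents do not show that stopping will differ between arms. This is a cheap improvement and does not by itself undermine the trial. It has to be settled before patients are treated, because the missing assessments cannot be made afterwards.

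**What to change.** Leave the Session 10 and 28-day visits as they are for patients who complete the course, on time or late. Moving everyone to the originally planned date would test late completers before their course ends and shorten their 28-day durability interval.

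Add one rule to the Aim 3 text and a matching footnote to the Schedule of Procedures. Every randomised patient who stops stimulation early and has not withdrawn consent still has the MDRS and MEG at the date on which Session 10 was planned, and the MDRS again 28 days after that date. Record the planned date when Session 1 is given. State in section IV.F that these patients are analysed in the group to which they were randomised. The rule concerns outcome collection only and says nothing about when stimulation should stop.

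The cost is a wording change and a few extra attendances at visits already budgeted, with no new procedures or patients. The estimate will then include the effect of partial treatment. On the assumptions above, this could lower the expected difference to as little as 9.1 points, with power between 72% and 80%. Patients who withdraw from the study will still be missing.
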